**Columbia University Medical Center**  
**Herbert Irving Comprehensive Cancer Center**  
**Version Date: 04/21/2021**

5.2.5 History of allergic reactions attributed to compounds of similar chemical or biologic composition to Turalio® or Sirolimus.

5.2.6 For Phase 2 - Prior exposure to a receptor tyrosine kinase or mammalian target of Rapamycin inhibitor.

5.2.7 Pregnant women are excluded from this study because Turalio® and Sirolimus are agents with the potential for teratogenic or abortifacient effects. Because there is an unknown but potential risk for adverse events in nursing infants secondary to treatment of the mother with Turalio® and Sirolimus, breastfeeding should be discontinued if the mother is treated with Turalio® and Sirolimus.

5.2.8 Uncontrolled intercurrent illness including, but not limited to, ongoing or active infection, active liver disease, symptomatic congestive heart failure, unstable angina pectoris, cardiac arrhythmia, or psychiatric illness/social situations that would limit compliance with study requirements.

5.2.9 Active secondary malignancy unless the malignancy is not expected to interfere with the evaluation of safety and is approved by the Sponsor. Examples of the latter include basal or squamous cell carcinoma of the skin, in-situ carcinoma of the cervix, and isolated elevation of prostate-specific antigen. Subjects with a completely treated prior malignancy and no evidence of disease for  $\geq 2$  years are eligible.

5.2.10 Major surgical procedure or significant traumatic injury within 14 days of initiating study drug or anticipation of the need for major surgery during the study.

5.2.11 Previous radiotherapy to 25% or more of the bone marrow and/or radiation therapy within 28 days prior to study entry.

5.2.12 Inability to swallow capsules, or refractory nausea and vomiting, malabsorption, an external biliary shunt, or significant bowel resection that would preclude adequate absorption.

5.2.13 Congestive heart failure (CHF) New York (NY) Heart Association class III or IV; unstable coronary artery disease (myocardial infarction [MI] more than 6 months prior to study entry is permitted); or serious cardiac arrhythmia.

5.2.14 Baseline QTcF  $\geq 450$  ms (males) or  $\geq 470$  ms (females)

5.2.15 HIV-positive patients on combination antiretroviral therapy are ineligible because of the potential for pharmacokinetic interactions with PLX3997. In addition, these patients are at increased risk of lethal infections when treated with marrow-suppressive therapy. Similarly, patients with chronic or acute hepatitis C virus (HCV) or hepatitis B virus (HBV) infection are also ineligible. Prior hepatitis infection that has been treated with highly effective therapy with

no evidence of residual infection and with normal liver function (ALT, AST, total and direct bilirubin  $\leq$  ULN) is allowed.

5.2.16 Of the five major CYP isoforms, 3A4 (BFC) may be involved in Phase I metabolism of Turalio®, with possibly CYP1A2 playing a minor role. Until information regarding exposure toxicity and exposure-response relationships are available with Turalio®, concomitant strong CYP3A4 inhibitors and inducers are not permitted in the event they alter the systemic exposure to Turalio® (see Attachment 1 for a list of common CYP3A4 inhibitors and inducers). These include anticonvulsants, mycin antimicrobials, and antiretrovirals. Some common examples include inhibitors such as erythromycin, fluoxetine, gemfibrozil, and inducers such as rifampicin, carbamazepine, phenytoin, efavirenz, and nevirapine.

If concomitant use with a strong CYP3A inhibitor, UGT inhibitor, or acid reducing agent cannot be avoided, see below for guidance taken from the approved USPI.

Avoid concomitant use of Turalio® with strong CYP3A inhibitors or UGT inhibitors during treatment with Turalio®. If concomitant use with a strong CYP3A inhibitor or UGT inhibitor cannot be avoided, reduce the Turalio® dose according to the recommendations in table below. If concomitant use of a strong CYP3A inhibitor or UGT inhibitor is discontinued, increase the Turalio® dose (after 3 plasma half-lives of the strong CYP3A inhibitor or UGT inhibitor) to the dose that was used before starting the inhibitor [see Clinical Pharmacology (12.3)].

| Recommended Dosage Reductions for Turalio® for Concomitant Use of Strong CYP3A Inhibitors or UGT Inhibitors |                                  |  |
|--|----------------------------------|--|
| Planned Total Daily Dose  | Modified Total Daily Dose | Administration of Modified Total Daily Dose |
| 800 mg   | 400 mg                           | 200 mg twice daily                                 |
| 600 mg   | 400 mg                           | 200 mg twice daily                                 |
| 400 mg   | 200 mg                           | 200 mg once daily                                  |

\* Planned total daily dose refers to recommended dose reductions for Turalio® for adverse reactions based on dosing recommendations in Section 8.2 Dose Modifications

Avoid the concomitant use of proton pump inhibitors (PPI) while taking Turalio®. As an alternative to a PPI, administer Turalio® 2 hours before or 2 hours after taking a locally-acting antacid, or if using a histamine 2 (H2)-

**Columbia University Medical Center**  
**Herbert Irving Comprehensive Cancer Center**  
**Version Date: 04/21/2021**

receptor antagonist, administer Turalio® at least 2 hours before or 10 hours after taking an H2-receptor antagonist.

Concomitant treatment is permitted if the medication is not expected to interfere with the evaluation of safety or efficacy of the study drug. During the study, if the use of any concomitant treatment becomes necessary (e.g., for treatment of an adverse event), the treatment must be recorded on the eCRF, including the reason for treatment, generic name of the drug, dosage, route, and start and stop dates of administration.

Sirolimus undergoes extensive hepatic and intestinal metabolism via CYP3A4 and CYP3A5, as well as excretion by P-glycoprotein. Strong CYP3A inhibitors such as ketoconazole or grapefruit juice are not permitted. Patients should be monitored for supratherapeutic toxic levels of Sirolimus and Turalio®. As bone marrow suppression including anemia, neutropenia, and thrombocytopenia have been reported in patients receiving Sirolimus monotherapy, these adverse effects may be exacerbated in combination with Turalio® for which patients will be closely monitored.

- 5.2.17. Any patients on warfarin therapy.
- 5.2.18. Hepatobiliary diseases including biliary tract diseases, autoimmune hepatitis, inflammation, fibrosis, cirrhosis of liver caused by viral, alcohol, or genetic reasons. Gilbert's disease is allowed if TBil is  $\leq 1.5 \times$  ULN.

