**Columbia University Medical Center**  
**Herbert Irving Comprehensive Cancer Center**  
**Version Date: 04/21/2021**

If concomitant use with a strong CYP3A inhibitor, UGT inhibitor, or acid reducing agent cannot be avoided, see below for guidance taken from the approved USPI

| Recommended Dosage Reductions for Turalio® for Concomitant Use of Strong CYP3A Inhibitors or UGT Inhibitors |                                  |  |
|--|----------------------------------|--|
| Planned Total Daily Dose  | Modified Total Daily Dose | Administration of Modified Total Daily Dose |
| 800 mg   | 400 mg                           | 200 mg twice daily                                 |
| 600 mg   | 400 mg                           | 200 mg twice daily                                 |
| 400 mg   | 200 mg                           | 200 mg once daily                                  |

\* Planned total daily dose refers to recommended dose reductions for Turalio® for adverse reactions based on dosing recommendations in Section 8.2 Dose Modifications

Avoid the concomitant use of proton pump inhibitors (PPI) while taking Turalio®. As an alternative to a PPI, administer Turalio® 2 hours before or 2 hours after taking a locally-acting antacid, or if using a histamine 2 (H2)-receptor antagonist, administer Turalio® at least 2 hours before or 10 hours after taking an H2-receptor antagonist.

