### 8.2.3 Dose Modification for Non-Hematologic Toxicity

Reduction/interruption of dosing for other AEs may take place at any time. Below are guidelines for dosage modification for Turalio®-related toxicities as well as guidelines for their management. Dose reductions should depend on the toxicity grade, as noted in Table 14. These parameters are only a guide and are not intended to supersede the clinical judgment of the treating physician. All adjustments should be made in consultation with the principal investigator. **Dosing holds longer than 21 days for any reason should generally result in discontinuation from the study**, unless the patient has demonstrated a clinical benefit from therapy and would like to continue dosing with study drug after discussion between the investigator and the Principal investigator.

| Toxicity Grade (CTCAE v4)   | Turalio® and Sirolimus dose changes during current treatment period                      | Dose adjustments for resumption of treatment  |
|---|--|---|
| Hematologic Toxicity   |  |   |
| Any Grade 4, or Grade 3, neutropenia with fever, or thrombocytopenia with bleeding, except for Grade 4 lymphopenia             |  |   |
| 1 st Appearance  | Interrupt until ANC recovers to $\geq 1 \times 10^9/L$ ; growth factor support permitted | Dose reduce Turalio® to 400mg orally in AM and 400mg orally in PM daily.  |
| 2 nd Appearance  | Interrupt until ANC recovers to $\geq 1 \times 10^9/L$ ; provide growth factor support   | If Turalio® total daily dose at 800mg orally, dose reduce Turalio® to 200mg in AM and 400mg in PM. If Sirolimus 2.0mg, decreased to 1.0mg.  |
| 3 rd Appearance  | Interrupt until ANC recovers to $\geq 1 \times 10^9/L$ ; provide growth factor support   | Discontinue study treatments unless subject deriving clinical benefit. Consult with Principal investigator and consider decreasing Turalio® to 200mg twice daily and decrease Sirolimus to half the dose unless at 0.5mg. |
| 4 th Appearance  | Discontinue Permanently  | N/A   |
| Non-Hematologic Related Grade 3 or Grade 4 not related to abnormal liver function (start symptomatic treatment when possible). |  |   |
| 1 st Appearance  | Interrupt until recovered (grade 0-1) and provide supportive management.                 | Dose reduce Turalio® to 400mg orally in AM and 400mg orally in PM daily and Sirolimus to 1.0mg orally in AM.  |

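### Item 5.2.16 bans strong CYP3A inhibitors, yet its fallback allows unavoidable use with a Turalio-only change, and the reduction table has no row for the Phase 2 dose of 1000 mg/day

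*Combined protocol and SAP*

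**What the plan says.** Item 5.2.16 in Section 5.2 (Exclusion Criteria) contains two prohibitions and one fallback.

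- **First prohibition.** Strong CYP3A4 inhibitors and inducers are disallowed because they may alter Turalio exposure.
- **Fallback.** The item then provides for the case where the drug is needed anyway: "If concomitant use with a strong CYP3A inhibitor or UGT inhibitor cannot be avoided, reduce the Turalio® dose", using a table. When the inhibitor stops, the instruction is to "increase the Turalio® dose (after 3 plasma half-lives of the strong CYP3A inhibitor or UGT inhibitor") to the dose used before. Both steps concern Turalio alone.
- **Second prohibition.** After the fallback, the item says "Sirolimus undergoes extensive hepatic and intestinal metabolism via CYP3A4 and CYP3A5", and then "Strong CYP3A inhibitors such as ketoconazole or grapefruit juice are not permitted". No exception is stated there.
- **Repeat.** The fallback and its table appear again, complete, just before Section 7.3.

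The table has three rows: 800 to 400, 600 to 400, and 400 to 200 mg/day. Its footnote reads "Planned total daily dose refers to recommended dose reductions for Turalio® for adverse reactions based on dosing recommendations in Section 8.2 Dose Modifications". Table 14 in Section 8.2.3 gives those reduced doses: "Dose reduce Turalio® to 400mg orally in AM and 400mg orally in PM daily"; "If Turalio® total daily dose at 800mg orally, dose reduce Turalio® to 200mg in AM and 400mg in PM"; and, at a third hematologic event, "consider decreasing Turalio® to 200mg twice daily". The assigned Phase 2 dose is 1000 mg/day of Turalio with 2 mg/day of sirolimus (Sections 4.1, 9.6.1 and 9.7).

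**The concern.** A site facing an unavoidable strong CYP3A inhibitor can find opposite instructions in the same item. If it takes the fallback, it is told how to lower and later restore Turalio and is told nothing about sirolimus, although the protocol itself describes sirolimus as cleared through CYP3A4 and CYP3A5.

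If the patient is at the assigned Phase 2 dose, the site is also sent to a table with no applicable row. This second problem does not depend on the first. UGT inhibitors fall under the fallback but outside the ban, so a starting-dose patient who needs one must have Turalio reduced to an unstated dose.

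What is at stake is patient safety and consistent dosing. Section 9.1.1 warns of serious and fatal liver injury with Turalio and says other medications may raise that risk. Section 9.1.2 lists fatal hepatic necrosis with sirolimus and links it to raised trough concentrations.

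**Working it through.** The plan states no figure on this point to reproduce. The check compares the rules and then does simple dose and day arithmetic.

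**1. The rules side by side**

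| Place | Strong CYP3A inhibitor | UGT inhibitor | Turalio | Sirolimus |
|---|---|---|---|---|
| 5.2.16, first prohibition | Not allowed | Not mentioned | Reason given: exposure | Not mentioned |
| 5.2.16, fallback (repeated before 7.3) | Avoid; allowed if unavoidable | Avoid; allowed if unavoidable | Reduce by table, restore later | Not mentioned |
| 5.2.16, second prohibition | Not allowed, no exception | Not mentioned | Monitor for toxic levels | Reason given: clearance; monitor for toxic levels |

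The first prohibition followed by the fallback could be read as a rule with an exception. The second prohibition comes after the fallback and restates the ban without that exception.

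**2. Sirolimus controls (Sections 8.2 and 8.2.1, Table 10)**

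Scheduled troughs fall on days 2, 8, 15 and 22 of cycle 1, then on day 1 of each 28-day cycle, that is, study days 29, 57, 85 and so on. The gaps are 8 − 2 = 6, then 7, 7 and 7, then 57 − 29 = 28 and 85 − 57 = 28 days. Extra troughs may be drawn when clinically needed, so 28 days is the scheduled spacing and not a worst-case delay.

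Table 10 acts once a level exceeds 18 µg/L. At a first event, if the level is 18 µg/L or lower after the three-day hold, sirolimus restarts at 2 mg, the assigned dose. The table does not ask whether an inhibitor is still being taken.

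**3. Coverage of the reduction table**

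- Assigned Turalio dose: 400 + 600 = 1000 mg/day (Section 9.6.1).
- Table 14 steps: 400 + 400 = 800; 200 + 400 = 600; 200 + 200 = 400 mg/day.
- Phase 2 levels: 1000, 800, 600, 400. Table rows: 800, 600, 400.
- Result: 3 of 4 levels have a row, and 1000 mg/day does not.

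The three rows are exactly the three reduced doses, as the footnote implies. The copy before Section 7.3 shows the table whole, so a row has not simply been lost.

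**4. Can the missing dose be inferred?**

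Share of the planned dose kept: 400/800 = 50%, 400/600 = 67%, 200/400 = 50%. The rows do not follow one ratio. Purely as an illustration, assume the same range applied at 1000 mg: 0.50 × 1000 = 500 mg and 0.667 × 1000 = 667 mg. With 200 mg capsules, 600 mg lies inside that range and 400 mg is the next total below it. These keep 60% and 40% of the dose, and 600/400 = 1.5. The documents do not choose between them.

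**5. Room within the existing hold**

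Section 8.2 lets either drug be held for any reason for up to 21 days. For assumed inhibitor courses of 7, 10 and 14 days, 21 − 7 = 14, 21 − 10 = 11 and 21 − 14 = 7 days remain for the three inhibitor half-lives that the fallback requires before the earlier Turalio dose is resumed. The half-lives depend on the inhibitor and are not given.

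**The case against.** The strongest reply is that the protocol can be followed safely as it stands. The fallback is conditional, so a site complies by obeying the ban. Sirolimus is described in Section 4.1 as dosed by trough, and Phase 2 uses 2 mg, the lowest level in Table 1. Item 5.2.16 itself asks for monitoring for toxic levels of both drugs. Visits are at least every other week in the first two cycles, extra troughs are allowed, Table 10 gives holds and reductions, and either drug may be held for 21 days. Guiding sirolimus by concentration is a legitimate alternative to reducing it in advance.

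Most of this stands, and it rules out several stronger readings a reader might infer:

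- **That the plan requires full-dose sirolimus with a strong inhibitor.** It does not. That combination arises only if a site takes the fallback, and even then a sirolimus hold is permitted.
- **That sirolimus is unprotected.** It is monitored. The gap is that nothing links monitoring or dose to the inhibitor, and the Table 10 change follows a high level.
- **That UGT inhibitors are ungoverned.** They are to be avoided, and Turalio reduced if they cannot be. Only the dose at 1000 mg/day is missing.
- **That sites would differ 1.5-fold.** The documents show no such divergence. The figure compares two plausible guesses.

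It is also fair that Section 6, Sections 7.1 and 7.2, Attachment 1 and Tables 5 and 11 were not in the text reviewed. A sirolimus instruction there cannot be excluded. It would not by itself reconcile the wording of 5.2.16 or fill the row missing from both table copies.

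**Conclusion.** The point holds as a safety and dosing inconsistency that should be fixed. Strong CYP3A inhibitors are prohibited twice and conditionally allowed in the same item. The allowance covers one of two study drugs although both prohibitions concern CYP3A, and the reduction table omits the dose every Phase 2 patient is assigned. The missing row is certain from the text. The absence of a sirolimus rule tied to the inhibitor is established only for the text reviewed.

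The reach is limited to patients among the planned 25 in Phase 2 who need an unavoidable inhibitor. The documents give neither how often that would happen nor how much exposure would change, so no event rate or exposure multiple is claimed. The 500 to 667 mg range rests on the assumption that the table's ratios extend upward. A reader might infer that the PFS analysis or the power is at risk; nothing in the documents supports that, and the sample size and stated power are unaffected.

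**What to change.** **(a) Make the rule consistent** in both prohibitions, the fallback and its repeat before Section 7.3. Choose one:

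- *The ban governs.* Remove strong CYP3A inhibitors from the fallback and from both table copies. For a short unavoidable course, hold study drug within the 21-day allowance, counting the three-half-life washout.
- *The exception stays.* State it in both prohibitions. Require a sirolimus hold or reduction, with a trough when the inhibitor starts and another when it stops.

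**(b) Add a 1000 mg/day row** to both table copies, with a dose confirmed by the sponsor's clinical pharmacology review. It is needed for UGT inhibitors under either choice in (a). A blanket Turalio hold at 1000 mg/day would be a poor substitute. A patient already reduced to 800 mg/day for toxicity would continue at 400 mg while one at the assigned dose received none, and long UGT-inhibitor use would outlast 21 days and generally force discontinuation.

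**Cost.** Amendment wording, one table line in two places, a site letter, and a few extra troughs if the exception is kept. If the ban governs, affected patients use part of their hold allowance, and a course too long for it would generally end study treatment. That matters to the individual: 21 days is half of the 6-week (42-day) median PFS assumed for standard care, since 21/42 = 0.5.

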**Columbia University Medical Center**  
**Herbert Irving Comprehensive Cancer Center**  
**Version Date: 04/21/2021**

If concomitant use with a strong CYP3A inhibitor, UGT inhibitor, or acid reducing agent cannot be avoided, see below for guidance taken from the approved USPI

| Recommended Dosage Reductions for Turalio® for Concomitant Use of Strong CYP3A Inhibitors or UGT Inhibitors |                                  |  |
|--|----------------------------------|--|
| Planned Total Daily Dose  | Modified Total Daily Dose | Administration of Modified Total Daily Dose |
| 800 mg   | 400 mg                           | 200 mg twice daily                                 |
| 600 mg   | 400 mg                           | 200 mg twice daily                                 |
| 400 mg   | 200 mg                           | 200 mg once daily                                  |

\* Planned total daily dose refers to recommended dose reductions for Turalio® for adverse reactions based on dosing recommendations in Section 8.2 Dose Modifications

Avoid the concomitant use of proton pump inhibitors (PPI) while taking Turalio®. As an alternative to a PPI, administer Turalio® 2 hours before or 2 hours after taking a locally-acting antacid, or if using a histamine 2 (H2)-receptor antagonist, administer Turalio® at least 2 hours before or 10 hours after taking an H2-receptor antagonist.

### **7.3 Duration of Therapy**

In the absence of treatment delays due to adverse events, treatment may continue until one of the following criteria applies:

- Disease progression
- Therapy may be permitted beyond progression if patient is deriving clinical benefit after initial tumor growth or ambiguity regarding the existence of disease progression in consultation with the principle investigator, sponsor, and CUMC IRB. If subsequent imaging confirms tumor growth, progression will be back dated to the prior scan. If patient agrees to treatment beyond progression, the patient will be required to sign a “Treatment Beyond Progression” informed consent form.
- Intercurrent illness that prevents further administration of treatment
- Unacceptable adverse events(s)
- Patient decides to withdraw from the study
- General or specific changes in the patient's condition render the patient unacceptable for further treatment in the judgment of the investigator
- Major protocol violation

#### **7.4 Duration of Follow Up**

Patients will be followed after completion or removal from study or until death, whichever occurs first. Patients removed from study for unacceptable adverse events will be followed until resolution or stabilization of the adverse event. Thereafter, patients will be contacted by phone every 3 months during year 1 and every 6 months thereafter to obtain information about subsequent treatment(s) and survival status.

#### **7.5 Criteria for Removal from Study**

The reasons a patient may discontinue or be withdrawn from the study include, but are not limited to, adverse event, clinically significant disease progression, patient request, investigator decision, protocol violation, patient noncompliance, and study termination by the Sponsor or institutional review board (IRB)/independent ethics committee (IEC).

When a patient discontinues or is withdrawn, the investigator will notify the Sponsor and should perform the procedures indicated in the End of Study column in the Schedule of Events within 28 days after discontinuation of study drug and before initiation of any new anti-cancer therapy. Follow-up information will be obtained for patients who discontinue their participation in or are withdrawn from the study.

Patients withdrawn from the study for reasons other than toxicity or clinically significant disease progression (e.g., protocol violation or noncompliance) may be replaced at the discretion of the medical monitor and the investigator. Study drug administration may be discontinued for an adverse event or at the discretion of the investigator.

The consequence of withdrawal of all consent by a patient will be that no new information will be collected from that patient and added to the existing data or any database. However, every effort will be made to follow all patients for safety.

